3.3.1.3 Sensitivity analyses

CAFS endpoints in Part A and Part B

[figure not shown]
To assess the impact of baseline characteristics in the comparison of CAFS scores between treatment groups, a sensitivity analysis using a similar rank ANCOVA model to adjust for baseline prognostic factors in the mITT population as mentioned in [Section 3.2.3](#) will be performed at Week 24, Week 76 and Week 104, respectively.

3.4 TERTIARY/EXPLORATORY ENDPOINT(S) ANALYSIS

Tertiary/exploratory endpoints in Part A and Part B are listed in [Table 1](#).

3.4.1 Definition of endpoint(s)

[figure not shown]
3.4.2 Main analytical approach

Missing data will not be imputed in the analysis of tertiary endpoints, nor will sensitivity or subgroup analyses be conducted.

For continuous endpoints, summary statistics including mean, standard deviation, median, interquartile range (Q1, Q3), minimum, and maximum will be provided for these continuous endpoints at scheduled visits in Part A and Part B. Only participants with baseline and post-baseline data will be summarized. Plots of mean (\pm SD) and/or mean change (\pm SD) and/or median over time will also be provided for better visualization. These continuous endpoints will also be analyzed using a similar MMRM approach as described for the primary endpoint in Part A in [Section 3.2.2](#), except that the baseline ALSFRS-R score will be replaced by the baseline values of

the corresponding endpoint. In addition, for the change from baseline in maximum phonation time on [REDACTED], age, height, and gender will also be included in the MMRM model as covariates. Plots of least squares means (\pm standard error) over time will be provided.

Time-to-event endpoints will be analyzed using the same manner as that used to analyze the secondary time-to-event endpoints in Part B in [Section 3.3.1.2](#).

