### Protocol amendment summary of changes table

Section # and Name	Description of Change	Brief Rationale
Synopsis	Route of administration for edaravone is changed from "intravenous" to "intravenous (IV) or oral"	Adding the oral formulation as it has been approved in the United States of America and China
Synopsis, Section 3 Objectives and Endpoints, Section 10.8.1.1 Study objectives and endpoints	In part B, deleting the text "before Week 52, Week 76, and Week 104" for the endpoints: time from baseline to the occurrence of either death or permanent assisted ventilation (>22 hours daily for >7 consecutive days), whichever comes first, time from baseline to the occurrence of death, time from baseline to the installation of a gastrostomy tube (G-tube)	To use all available data up to the time of cutoff
Synopsis, Section 1.3.1 Schedule of Activities. Part A, Section 2.2 Background, Section 4.1 Overall design, Section 5.1 Inclusion criteria, Section 6.3 Measures to minimize bias: randomization and blinding, Section 6.8 Concomitant therapy, Section 7.1.1 Permanent discontinuation, Section 9.4.2 Primary endpoint(s) in Part A, Section 9.4.3 Secondary endpoint(s) in Part A	The texts for noninvestigational medicinal products are changed to include the combination of sodium phenylbutyrate and taurursodiol (taurusodiol is also known as ursodoxicoltaurine).	The combination of sodium phenylbutyrate and taurursodiol is included as a standard of care for ALS in countries where it has been approved
Synopsis, Section 9.4.2 Primary endpoint(s) in Part A	The sentence "The model will also include a random intercept and slope" is deleted	Clarification of terms in the MMRM model
Synopsis, Section 9.4.3 Secondary endpoint(s) in Part A	For the main secondary endpoints in Part A, the text for continuous variables is changed to include baseline NfL (if different from the baseline value of the endpoint), use of the combination of sodium phenylbutyrate and taurursodiol, baseline value of endpoint-by-visit interaction, and baseline NfL-by-visit interaction (if different from the baseline value of the endpoint-by-visit interaction).	Clarification of terms in the MMRM model

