3.3.1.2 Main analytical approach

Treatment policy will be used for the analyses of all secondary endpoints in Part A and Part B as stated in [Table 2](#).

CAFS

CAFS at Week 24, Week 76 and Week 104 will be analyzed in the same manner as that used to analyze the primary endpoint in Part B in [Section 3.2.2](#).

Continuous Endpoints

Continuous endpoints include:

Part A

- change from baseline in SVC to Week 24
- change from baseline in muscle strength to Week 24
 - change from baseline in megascore to Week 24
 - change from baseline in grip strength to Week 24
- change from baseline in ALSAQ-5 to Week 24
- change from baseline in serum NfL to Week 24

Part B

- change from baseline in the ALSFRS-R total score to Week 52, Week 76, and Week 104
- change from baseline in SVC to Week 52, Week 76, and Week 104
- change from baseline in ALSAQ-5 to Week 52, Week 76, and Week 104
- change from baseline in serum NfL to Week 52

These continuous endpoints will be analyzed using the same manner as that used to analyze the primary endpoint in Part A in [Section 3.2.2](#), except that baseline ALSFRS-R score will be replaced by the baseline value of the corresponding endpoint. Plots of least squares means (\pm standard error) over time will be provided. Plots of mean (\pm SD) and/or mean change (\pm SD) and/or median over time will also be provided. For NfL data, log transformation will be applied in

the MMRM model. The treatment difference will then be back-transformed to the original scale. The back-transformed LS means stand for geometric mean ratios compared to baseline, and the back-transformed LS means difference stands for ratio of the geometric mean ratios compared to baseline between SAR443820 and placebo. In order to assess the impact of deviation from the normality assumption, a sensitivity analysis using rank analysis of covariance (ANCOVA) with the same covariates as for the MMRM analysis except visit and related interaction terms, will be performed to provide the p-value for the comparison between the treatment groups.

Time-to-event endpoints

Time-to-event endpoints in Part B include:

[figure not shown]
- time from baseline to occurrence of either death or permanent assisted ventilation (>22 hours daily for >7 consecutive days), whichever comes first
- time from baseline to the occurrence of death

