For the time-to-event endpoints, baseline is defined as randomization. The time to event will be modeled by a Cox proportional hazards model. The covariates included in the model are treatment group, randomization strata of the geographic region of the study site, ALS onset region (bulbar or other areas), use of riluzole (yes or no), use of edaravone (yes or no), use of the combination of sodium phenylbutyrate and taurursodiol (yes or no), disease duration (from first symptom onset to the screening visit), baseline ALSFRS-R score and baseline NfL. The hazard ratio between SAR443820 and placebo, its 95% confidence interval and the p-value for comparing SAR443820 and placebo will be estimated from this model with robust variance estimation (9). Comparison between SAR443820 and placebo will also be assessed by a log-rank test stratified by randomization strata of the geographic region of the study site, ALS onset region (bulbar or other areas), use of riluzole (yes or no), use of edaravone (yes or no), use of the combination of sodium phenylbutyrate and taurursodiol (yes or no) and baseline NfL (< median baseline NfL or >= median baseline NfL). Kaplan-Meier (KM) plots of the cumulative incidence rate will be provided by treatment group to depict the course of occurrence of event over time. The proportion of participants with events at given time points (eg, Week 4, 8, 12, 16, 20, 24, etc.) and median time to event (if feasible) will be calculated using the KM estimates.

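### No visible rule says how death before a gastrostomy tube is handled; under ordinary Kaplan-Meier it would be censored, and the reported tube incidence would be too high (minor)

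*SAP*

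**What the plan says.** For the tertiary endpoints, SAP 3.4.2 states: "Time-to-event endpoints will be analyzed using the same manner as that used to analyze the secondary time-to-event endpoints in Part B". It plans no sensitivity analysis for them.

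The method it points to is in SAP 3.3.1.2, which covers two endpoints: "time from baseline to occurrence of either death or permanent assisted ventilation", and "time from baseline to the occurrence of death". For these, the SAP specifies:

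- a regression: "The time to event will be modeled by a Cox proportional hazards model";
- a stratified log-rank test;
- curves: "Kaplan-Meier (KM) plots of the cumulative incidence rate will be provided by treatment group";
- event proportions at given time points and the median, which "will be calculated using the KM estimates".

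The change log for protocol amendment 02 (Protocol 10.13.3) names a third Part B time-to-event endpoint, "time from baseline to the installation of a gastrostomy tube (G-tube)". That amendment removed only the week limits from the endpoint, so that all data up to the cutoff could be used. The endpoint is not in the visible primary or secondary lists of either document. The tertiary rows of the objectives tables are redacted, and the tertiary definitions in SAP 3.4.1 are not visible. The log is used here only to identify the endpoint, not as evidence of a contradiction.

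**The concern.** Both secondary endpoints count death as an event, so death cannot compete with either of them, and KM is the right estimator. Time to tube placement, as named, does not count death, and a participant who dies can no longer have a tube placed. If the method is carried over unchanged, the ordinary KM treatment of a death without a tube is censoring. In that case 1 minus KM estimates how many would receive a tube if nobody died, whereas the SAP presents it as a cumulative incidence and as the proportion of participants with events.

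Death is not rare in this setting. Protocol 2.2 says most patients die within 3 to 5 years of onset, entry is allowed up to 2 years after onset, and follow-up runs to Week 104. The Protocol (3.1.1) already accepts the principle for function: it justifies the CAFS because mortality confounds functional outcomes. At stake is a descriptive curve and its proportions, which would be too high, and more so in the arm with more deaths.

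**Working it through.** **Plan figures.** The documents give no tube rate, death rate or cumulative incidence, so there is no figure of the plan's own to reproduce. The arm sizes, 174 and 87, come from SAP 1.1. All rates below are assumptions.

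**Formulas.** Assume constant cause-specific hazards. Let g be the tube risk by Week 104 if there were no deaths, and d the death risk by Week 104 if there were no tubes. Put a = -ln(1-g), b = -ln(1-d), and let t be the fraction of 104 weeks elapsed.

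- 1 minus KM, with deaths censored: 1 - exp(-a t)
- Actual cumulative incidence (the Aalen-Johansen target): a/(a+b) × [1 - exp(-(a+b) t)]

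**One case in full, g = d = 0.30, Week 104.** a = b = 0.357.

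- 1 minus KM = 30.0%.
- Cumulative incidence = 0.5 × (1 - 0.70 × 0.70) = 0.5 × 0.51 = 25.5%.
- Excess = 4.5 points.

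**Excess of 1 minus KM at Week 104, in points**

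| Tube risk g | d = 20% | d = 30% | d = 40% |
|---|---|---|---|
| 20% | 2.0 | 3.1 | 4.2 |
| 30% | 2.9 | 4.5 | 6.2 |
| 40% | 3.8 | 5.8 | 8.0 |

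**Earlier time points, with g = d**

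| g = d | Week 24 | Week 52 | Week 104 |
|---|---|---|---|
| 20% | 0.1 | 0.6 | 2.0 |
| 30% | 0.3 | 1.3 | 4.5 |
| 40% | 0.6 | 2.5 | 8.0 |

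**Simulation check.** In 2000 simulated trials with n = 261 and g = d = 30%, mean 1 minus KM was 30.1% and mean Aalen-Johansen 25.6%. The first was higher in every run, with a smallest gap of 2.2 points. With the two risks positively correlated through a shared frailty, the means were 31.3% and 26.4%. The direction therefore does not depend on independent risks.

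**Arm difference.** Give both arms the same tube hazard, so that 1 minus KM shows no difference, and let only deaths differ. The shift is the difference in actual cumulative incidence. The standard error (SE) combines, over n = 174 and n = 87, the large-sample KM variance (1-g)² × a × (exp(a+b) - 1) / ((a+b) n). It assumes no dropout.

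| g (both arms) | Deaths 25% vs 35% | Deaths 20% vs 40% |
|---|---|---|
| 20% | 1.1 points (0.19 SE) | 2.2 points (0.4 SE) |
| 30% | 1.6 points (0.24 SE) | 3.2 points (0.5 SE) |
| 40% | 2.1 points (0.3 SE) | 4.2 points (0.6 SE) |

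For g = 30% with deaths of 20% vs 40%, the actual incidences are 27.1% and 23.8%. The largest entry is 0.58 to 0.595 SE, depending on which arm has more deaths, so every shift stays below 0.6 SE. Dropout would enlarge the SE and lower these multiples.

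**The case against.** The strongest objection is that the deciding text cannot be read. The visible SAP gives no censoring rule for these endpoints, and the section that defines them is not visible. The hidden definition could combine the tube with death, or state how deaths are handled. Either would remove the problem, and redacted text cannot be counted as missing from the plan. The endpoint itself is also inferred: its name comes from a December 2022 change log, three amendments followed, and its tertiary status rests on its absence from the visible lists. This stands, and it makes the point conditional. A reader might infer that the plan demonstrably censors death before the tube. The documents do not show that. They show a method with no visible place for such deaths, and censoring is what ordinary KM would then do.

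A reader might also infer that the treatment comparison is invalid. That does not follow. With deaths censored, the Cox model and log-rank test remain valid comparisons of cause-specific hazards, and only the curve, the proportions and the median change meaning. Nor is Aalen-Johansen a purer measure of drug effect, because an arm with more deaths will show fewer tubes. That is why deaths without a tube belong beside it.

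The remaining objections concern size, and they also stand. The time points that SAP 3.3.1.2 gives as examples run only to Week 24, where the excess is a fraction of a point. The endpoint lies outside the Part A testing hierarchy in SAP 3.5. It belongs to an open-label part planned with active drug for everyone still eligible for dosing, and dosing there has been paused since December 2023.

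**Conclusion.** The point holds as a conditional, minor one. SAP 3.4.2 sends every tertiary time-to-event endpoint to a method built for endpoints that include death, and at least one endpoint named in the protocol's history does not include it. If death before the tube is censored, 1 minus KM overstates the proportion who receive one. Under constant hazards and assumed risks of 20-40%, the overstatement matters mainly late in Part B, at about 2 to 8 points by Week 104. The effect on the arm difference is modest, about 1 to 4 points and under 0.6 SE, and it needs mortality to differ between arms by 10 to 20 points.

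The conclusion rests on two inferences that the visible text does not settle: that time to tube is still a tertiary endpoint, and that its hidden definition neither counts death nor sets a rule for it. The primary result, sample size, alpha and testing hierarchy are untouched.

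**What to change.** Add to SAP 3.4.2: for any tertiary time-to-event endpoint that death precludes and that does not count death as an event, death is a competing event. For such endpoints:

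- report Aalen-Johansen cumulative incidence curves and proportions by arm in place of 1 minus KM;
- label the Cox and log-rank results as cause-specific;
- show deaths without a tube beside them, by arm.

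The wording is conditional, so it does no harm if the redacted definition already includes death. It costs one sentence and a standard option in SAS PROC LIFETEST, with no change to data collection. The reported tube proportions would be somewhat lower.

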3.4.3 Comparison with external control

A matched analysis using data from historical clinical trial database (for example, PROACT) as a control will be conducted to demonstrate the superiority of SAR443820 on slowing down disease progression and prolonging survival over 104 weeks of treatment period.

Matching procedure

1. Pre-matching filtering: The participants in the historical clinical trial database will be filtered by the following factors that match our trial eligibility criteria and duration:
 - Age 18 – 80 years, inclusive
 - First ALS symptom onset ≤ 2 years
 - Baseline SVC (%) $\geq 60\%$
 - Baseline ALSFRS-R decline rate $\geq 0.5/\text{month}$
2. Propensity score matching: Propensity score matching seeks to balance the distributions of known prognostic covariates in treatment and control group to resemble what would occur had the treatment been randomly assigned. A logistic regression for the treatment group as the dependent variable is performed to obtain the propensity score with the abovementioned matching variables, using all the participants (planned for 174) randomized to the SAR443820 arm and the participants from the historical clinical trial database after filtering as described above. Each participant in the SAR443820 treated group will be matched 1:1 using the Mahalanobis distance to a participant in the historical clinical trial database. Matching will be performed with replacement.

To assess the success of the matching procedure, summary statistics of baseline matching variables will be presented and compared between the two treatment groups before and after matching to assess post-match balance.

Post-matching statistical analysis

Once the matching is performed, the comparison between participants who were randomized to SAR443820 and placebo arm generated from the historical trial database will be provided for the following endpoints using the similar analyses models as described for the primary and secondary endpoints in [Section 3.2.2](#) and [Section 3.3.1.2](#).

- Combined assessment of function and survival (CAFS) score at Week 52, Week 76, and Week 104
- Change from baseline in ALSFRS-R total score to Week 52, Week 76, and Week 104
- Time from baseline to the occurrence of either death or permanent assisted ventilation (>22 hour daily for >7 consecutive days) whichever comes first
- Time from baseline to the occurrence of death

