## 2.2 BACKGROUND

ALS is a fatal neurodegenerative disorder characterized by progressive loss of motor neurons in the cortex, brain stem, and spinal cord. Relentless and progressive muscle atrophy and weakness are hallmarks of ALS. Most patients with ALS die from respiratory failure within 3 to 5 years after disease onset. Among the 3 Food and Drug Administration (FDA)-approved ALS treatments, riluzole and edaravone demonstrate only a moderate effect either on survival or functional decline, respectively, and more data is needed to further support the treatment effect of the recently approved treatment, the combination of sodium phenylbutyrate and taurursodiol. Therefore, there is still a significant unmet medical need for treating individuals with ALS.

SAR443820 has demonstrated strong RIPK1 inhibition with high potency in vitro in various cell types. Refer to the SAR443820 Investigator's Brochure (IB) for a detailed description of the chemistry, pharmacology, efficacy, and safety of SAR443820.

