#### **9.4.5 Tertiary endpoints**

Methods for analysis of tertiary endpoints will be included in the SAP. A matched analysis using data from the Phase 3 clinical trial for Ceftriaxone (NCT00349622) as a historical control might be conducted to demonstrate the superiority of SAR443820 on slowing down disease progression and prolonging survival over 104 weeks of treatment period.

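### The tertiary external-control comparison aims to demonstrate superiority, but it cannot separate drug effect from residual between-trial difference and does not use the randomised placebo arm to calibrate the historical control

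*SAP*

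**What the plan says.** SAP 3.4.3 states that a matched analysis against a historical trial database "will be conducted to demonstrate the superiority of SAR443820 on slowing down disease progression and prolonging survival". Protocol 9.4.5 is less firm: the analysis "as a historical control might be conducted to demonstrate the superiority of SAR443820", and the source is one named phase 3 trial.

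Historical participants are filtered on age, symptom duration, SVC and pre-study decline rate. A propensity model is then fitted "using all the participants (planned for 174) randomized to the SAR443820 arm", followed by 1:1 Mahalanobis matching with replacement. After matching, the "comparison between participants who were randomized to SAR443820 and placebo arm generated from the historical trial database will be provided" using models similar to those of SAP 3.2.2 and 3.3.1.2. The listed endpoints are:
- CAFS at three late visits, given as "Combined assessment of function and survival (CAFS) score at Week 52, Week 76, and Week 104"
- ALSFRS-R at the same three visits, given as "Change from baseline in ALSFRS-R total score to Week 52, Week 76, and Week 104"
- two survival endpoints: time to death or permanent assisted ventilation, and time to death alone

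The one check described is a before-and-after comparison of the baseline matching variables. SAP 3.4.2 rules out sensitivity analyses for tertiary endpoints. SAP 3.5 leaves this comparison outside the hierarchical testing procedure. SAP 1.1 gives the planned arms as 174 on SAR443820 and 87 on placebo, with Part A ending at Week 24.

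**The concern.** In a randomised comparison, a zero drug effect means a zero expected difference. Here it does not. The expected difference is the drug effect plus whatever separates this trial from the historical ones after matching and adjustment, such as era, sites, supportive care or rating practice.

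Background treatment is one plausible route. Protocol 2.2 says "riluzole and edaravone demonstrate only a moderate effect either on survival or functional decline" and describes a third approved product as recent. If this trial's participants decline more slowly than their historical matches for such reasons, the difference would look like benefit from SAR443820.

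Baseline balance cannot reveal this, because it concerns the matched variables and not the outcome. The trial does hold outcome data that could. Placebo participants matched to the same database should differ from their matches up to Week 24 only through bias and chance. The plan defines no such contrast, yet it states the aim as demonstrating superiority.

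**Working it through.** **The plan's own figures.** The arm sizes reproduce: 261 × 2/3 = 174 and 261 / 3 = 87. SAP 3.4.3 gives no power, error rate or bias figure for the external comparison. The placebo change and SD behind the sample size are redacted, so every SD and drift below is an assumption.

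**False rejection at Week 52 with no drug effect.** This treats the test as an unadjusted two-sample comparison with distinct controls.
- SE = SD × √(2/174)
- Shift = 12 months × drift
- Rejection = Φ(shift/SE − 1.96) + Φ(−shift/SE − 1.96)

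For example, SD 7 gives SE = 0.75. Drift of 0.1 points/month gives a shift of 1.2, a ratio of 1.60 and rejection of 0.36.

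| Drift (points/month) | Shift at Week 52 | SD 7 | SD 9 | SD 11 |
|---|---|---|---|---|
| 0 | 0 | 5% | 5% | 5% |
| 0.10 | 1.2 | 36% | 24% | 17% |
| 0.15 | 1.8 | 67% | 46% | 33% |
| 0.20 | 2.4 | 89% | 70% | 53% |

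With 20% dropout (139.2 per group) the three drift rows become 15–30%, 28–57% and 44–82%.

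**Cross-check in SD units.** Take 80% power, a 30% reduction, 2:1 allocation and 20% dropout. A closed-form calculation gives a detectable difference of (1.96 + 0.84) × √(1/69.6 + 1/139.2) = 0.411 SD. The implied placebo decline at Week 24 is 0.411/0.30 = 1.37 SD. Residual drift equal to 10% or 20% of that decline (0.137 or 0.274 SD) gives rejection of 25% or 73% with 174 per group, and 21% or 63% with 139 per group. A simulation of 1:1 Mahalanobis matching with replacement on four assumed covariates, with pools of 400 to 2000, gave 3–6% at no drift, 28–35% at 10% and 79–80% at 20%.

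**Survival, also illustrative.** For a residual between-trial hazard ratio of 0.8, the noncentrality is √(events/4) × |ln 0.8|. Rejection is 12%, 20% and 28% with 50, 100 and 150 events.

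**What a Week 24 placebo check could deliver.** Half-width = 1.96 × SD × √(2/87):
- 1.19, 1.49 and 1.78 points at SD 4, 5 and 6
- 1.33, 1.66 and 1.99 points after 20% dropout (69.6 per group)

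Week 24 is about 5.5 months. Drifts of 0.1, 0.15 and 0.2 therefore imply differences of 0.55, 0.83 and 1.10 points, all smaller than the half-width. As a significance test, the check would have power of about 9–15% at 0.1 and 23–44% at 0.2, before dropout.

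**The case against.** **The comparison is adjusted.** A reader might infer that the test responds to any difference between trials and that background drugs are ignored. The documents do not support that. Filtering and matching address four prognostic variables. The models of SAP 3.2.2 and 3.3.1.2 also adjust for region, riluzole, edaravone, the phenylbutyrate/taurursodiol combination, onset region, disease duration, baseline ALSFRS-R and baseline NfL. Three limits remain:
- The models are only described as similar, and the documents do not show that the historical data hold these variables.
- SAP 3.2.2 drops a stratification factor that has a level with fewer than 10 participants.
- The CAFS test is an unadjusted Wilcoxon-Mann-Whitney test. The rank ANCOVA for CAFS is in SAP 3.3.1.3, which SAP 3.4.3 does not cite.

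Era, site, care and rating differences are not covered by any of this.

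**Week 24 is not wholly absent.** The repeated-measures model uses all visits and yields least-squares-mean plots over time. The Kaplan-Meier output in SAP 3.3.1.2 includes Week 24. If the similar models keep these outputs, a Week 24 result may appear. What is missing is a listed contrast and any use of the placebo arm. Placebo participants who finish Part A after the December 2023 pause and enter Part B undosed also give some later information, but they are a selected, open-label subset.

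**No decision rests on it.** A reader might infer that a significant result would be declared as superiority of the drug. There is no decision rule here, the analysis is tertiary, and Protocol 9.1 ties a positive study to the Part A primary endpoint alone. This limits the consequence but does not justify the stated aim.

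**The magnitude is assumed and the remedy is imprecise.** Both are true. The documents give neither the drift nor its direction, and the calculation is unadjusted.

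**Conclusion.** The point holds in a limited form. SAP 3.4.3 sets a superiority aim for a non-randomised comparison whose estimate combines drug effect with residual between-trial difference. Its only validity check cannot see that difference, and the concurrent placebo arm is left out of the calibration.

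The 17–89% range shows how sensitive such a test is to modest drift. It rests on assumed SDs of 7–11, drifts of 0.1–0.2 points per month favouring this trial, 174 complete pairs and no covariate adjustment. It is not an estimate of this trial's error rate.

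A further inference to avoid is that a Week 24 placebo check would directly measure the bias in the later results. Its interval is wider than the biases considered, and bias at Week 24 need not equal bias at Weeks 52 to 104. It is still the only calibration available from a blinded, whole untreated arm. The Part A confirmatory conclusion is not affected.

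**What to change.** Amend SAP 3.4.3 as follows.

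1. Add Week 24 to the listed CAFS and ALSFRS-R external comparisons.
2. Apply the identical filter, matching and models to the randomised placebo participants over Weeks 0–24. Report the placebo-minus-historical difference with its 95% CI beside the SAR443820-minus-historical and the randomised Week 24 estimates. Present it as an estimate, not a pass/fail test. State that an interval covering zero does not show absence of bias, and that bias at Week 24 need not carry over to Weeks 52–104.
3. Replace the aim of demonstrating superiority with one of describing the difference, and interpret the later-week results alongside this calibration.

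The cost is a SAP wording change and one further run of the planned matching procedure, using trial data already collected. The downsides are an imprecise check and a weaker stated aim.
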